Recently, data have emerged suggesting that computational modelling of a patient's heart based on 3D MRI reconstructions can enable prediction of optimal targets for VT ablation non-invasively. This has been confirmed in both retrospective and prospective studies.⁸ This involves high resolution MRI imaging with late-gadolinium enhancement (LGE) to assess the three-dimensional geometry of the scar, followed by reconstruction of the patient's heart *in silico*^{9,10}. Fibre orientation is established and overlaid onto this model¹¹. Standard electrophysiological properties are applied to the different categories of tissue as defined by the LGE signal intensity, namely, normal tissue, scar and grey zone. Using computational modelling, this "virtual heart" is then analysed for different potential ventricular tachycardia circuits that are theoretically sustainable based on the information supplied. A virtual electrophysiology study with programmed stimulation is conducted by virtually pacing the heart model from various different locations⁹. An algorithm is used to predict optimal ablation sites to terminate all possible VT circuits in this model heart. The algorithm initially generates "primary sites", which are the initial locations which have the potential to sustain ventricular tachycardia in the patient's heart. The model then undergoes virtual VT ablation of these primary sites and the prediction algorithm is re-run. This may generate a new VT-sustaining substrate and give predictions of "secondary sites" which can sustain VT in the post-ablation heart. The process is repeated until the heart is no longer VT-inducible.¹². In this way, not only should the patient's clinical VT be ablated, but all future potential ventricular tachycardias supportable by the substrate in its current form should also be avoided, reducing the need for repeat VT ablation.

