2 RATIONALE

Current invasive substrate mapping techniques are time and labour intensive. The ability to identify arrhythmogenic from non-arrhythmogenic areas within the same scar is limited, leading to prolonged procedure time and the potential overuse of ablative energy. Activation mapping during ventricular tachycardia, the gold standard for defining the critical isthmus sustaining the arrhythmia, is significantly limited by hemodynamic instability.

Image-guided VT ablation has been shown to improve substrate definition and may underpin improved outcomes in certain patient populations^{13,14}. Given the newly emerging field of personalised medicine and computation modelling this study will help to assess if an MRI-based, computer generated model accurately correlates to the invasive findings from an EP study with regards to targeting ablation in VT. If the model proves to be accurate, this will help to advance the process of *in silico* planning of VT ablation and potentially lead to improvements in outcomes of VT ablation, as well as reducing the need for repeated procedures. Results from the invasive studies can also be fed back into the computational model in an attempt to improve its accuracy. Furthermore, by assessing the electrophysiological properties of the computer generated predicted sites, we may learn which signals may indicate a critically important part of the VT circuit which traditional electroanatomical maps may miss.

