4.2 Outcome

- Assessment of the degree of validation of *in silico* computational modelling by invasive ventricular scar interrogation to see if the predicted sites match those sites which would have been determined as important from invasive mapping.
- Qualification of the electrophysiological characteristics of those sites which the computational model predicted in an attempt to see what it is about them that makes them likely to be key to maintaining the arrhythmia. With our mapping techniques, we can assess not only the amplitude and morphology

of the electrograms from these areas, but also the directionality of wavefronts to see if this is an important feature. With the additional benefit of the 3D computational model, we may be able to gain some insight into the 3D nature of channels which form part of the VT substrate.

- Assessment of the change in the invasive electrophysiological characteristics of distant sites following ablation of the primary predicted *in silico* sites. By ablating the predicted areas, it is possible that when we re-map distant points, they may be a change in their electrophysiological properties. There may be a change in variables such as the stim-QRS latency, the QRS morphology, the capture threshold and the nature of the exit site (e.g. multiple-exit site changing to single-exit site).
- Assessment of the frequency of ventricular arrhythmia, frequency of therapy delivered from an ICD (if applicable) and duration until first delivered therapy on serial heart rhythm monitors. Also assessment of patient's symptoms and adverse effects on clinical consultation.

5 STUDY DESIGN and METHODS of DATA COLLECTION AND DATA ANALYSIS

The study will be a single centre, prospective study based at St George's University Hospitals NHS Foundation Trust in London. Consecutive patients presenting to the hospital with an appropriate scar-dependent, sustained monomorphic ventricular tachycardia, requiring catheter ablation, will be screened for inclusion into the study. Full inclusion and exclusion criteria are listed below. Patients are likely to be predominantly outpatients, requiring elective VT ablation, however inpatients may also be included in the study.

If found eligible for the study, the patient will be approached by one of the study investigators and a Patient Information Sheet (PIS) will be offered. Written consent will be obtained if the patient is willing to proceed.

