If included in the study, de-identified, anonymized MRI images from patient's routine scan will be transferred to Johns Hopkins University, Baltimore Maryland, for computational analysis. The patient's MRI images will be reconstructed, analysed and a 3D geometric model of the patient's heart formed. From this, a computer-generated model of the patient's heart will be created. As described above, a virtual EP study, VT ablation and generation of both primary and secondary sites will be generated. The computation model as well as the locations of these primary and secondary sites will again be stored securely and transferred back to the primary research centre.

The patient will then undergo traditional endocardial, and in appropriate cases, epicardial, mapping and ablation of ventricular tachycardia, using the techniques previously described ^{1-3,7,15}. Patient preparation on the day of the procedure will be as for any other clinical VT ablation. Ablation technique will depend on whether or not there is a documented 12 lead ECG of the patient's clinical VT and also whether or not the VT is haemodynamically tolerated (stable) or not (unstable). This will be decided by the operator and will follow usual practice for VT ablation.

We will use a multipolar mapping catheter, in order to create a high-density map and gain as detailed information as possible about the substrate. Multipolar catheters are used as standard of care for VT mapping and ablation in our institution and most other high-volume specialised centres. The 3D computational model will be merged with the traditional 3D electroanatomical map generated during the VT ablation. Particular care will be taken when mapping the points of interest from the computational prediction to assess their particular electrophysiological properties. This will allow us to assess variables such as wavefront directionality, amplitude and morphology to see if they have a particular signal which marks them as important in sustaining the VT circuit and therefore conferring their importance in predicting potential sites for ablation. By overlaying the computer generated model onto the invasive map, we will be able to corroborate the predicted model's findings with traditional mapping techniques.

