Ablation technique will be as per standard of care and the order of ablation will be guided by standard invasive mapping. However if we ablate at an area which the MRI-model also predicted to be important, we will re-map the surrounding myocardium to see if there has been an effect of the electrophysiological properties of these distant sites following ablation of the predicted sites.. The computer model will not alter the extent of ablation and will not lead to ablation of any areas which wouldn't otherwise be ablated using traditional mapping.

The patients will be followed up as standard of care at 3, 6 and 12 months following their procedure with ICD interrogation, or in the case of absence of an ICD an extended ECG monitoring period. We will use this to assess frequency and duration of recorded arrhythmias time to recurrence of ventricular arrhythmia as well as frequency of therapy delivered by the device. We will also use data from their clinical consultation to evaluate their symptoms and response to the procedure including any adverse events.

STUDY FLOW CHART

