6 STUDY SETTING

The study setting is a large tertiary centre hospital in London, St George's University Hospitals NHS Foundation Trust which serves a population of around 1.3 million. It also receives referrals from district general hospitals around it including in London, Surrey and Sussex. The patient population is diverse and referrals are made to a

specialist arrhythmia clinic from which suitable patients can be identified. The majority of recruited patients are expected to be outpatients who are symptomatic from VT despite optimal medical therapy. This will allow sufficient time to perform the cardiac MRI and to generate the computational model. In some scenarios, emergency admissions with symptomatic VT may be included if they are suitable for inpatient VT ablation and there is sufficient time for the MRI and computation analysis to take place prior to the VT ablation. All patient recruitment, consent, imaging and ablation will be performed at the single study centre.

The MRI images will be transferred to Johns Hopkins University in Baltimore, Maryland, USA for computational analysis and predictive modelling. This information will be securely transferred and on completion will be transferred back to the investigators for analysis.

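### The agreement outcome and the ablation limit both rest on what standard mapping alone would show, but the text shown does not require that result to be fixed before the predictions are revealed

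*Combined protocol and SAP*

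**What the plan says.** Model accuracy is the first aim in section 4. The first outcome in section 4.2 is an assessment "to see if the predicted sites match those sites which would have been determined as important from invasive mapping". Section 5 adds that the model "will not lead to ablation of any areas which wouldn't otherwise be ablated using traditional mapping", and sections 8 and 8.1 repeat that limit in other words. Both statements refer to what standard mapping would have shown on its own.

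On timing, section 5 has the model and its predicted locations returned to the centre, with mapping and ablation following. Section 6 says the modelling output "on completion will be transferred back to the investigators for analysis". It admits emergency patients only if "there is sufficient time for the MRI and computation analysis to take place prior to the VT ablation", and says the mainly outpatient population leaves time to build the model.

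On the procedure, section 5 states: "The 3D computational model will be merged with the traditional 3D electroanatomical map generated during the VT ablation". It then says: "Particular care will be taken when mapping the points of interest from the computational prediction". The stated purpose of that care is to characterise the electrical properties of those points. Section 8.1 places co-registration, extra mapping of predicted targets, and remapping after their ablation inside the procedure, with a maximum extension of 10%.

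**The concern.** The reference for the first outcome is counterfactual: it is the result standard mapping would have given without the model. That result can be known only if it is recorded before the predictions can affect where the catheter goes or how a signal is judged.

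If predicted areas are sampled more closely, or read by someone who knows they were predicted, abnormal signals there may be found and called important more often, which would favour the model. Closer mapping can also clear a site that looked abnormal on a sparser map, so the net effect is not certain. All patients, at least 20 by section 7.2.1, would go through the same sequence.

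The ablation limit has a related but smaller problem. Operators can follow it, but without a record of the targets chosen before the predictions were seen, nobody can fully check afterwards that they did.

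**Working it through.** This is a question of sequence and masking. The documents give no agreement measure, matching distance, expected match rate, power or precision target, so there is no figure of the plan's own to reproduce. The text was checked in four steps.

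1. **Are the predictions available before mapping?** Yes, at the centre (sections 5 and 6). Section 7.3.1 says the site research team also belongs to the clinical team, but in the context of eligibility screening. It does not identify the operator.
2. **Are they used during the case?** Yes. They are merged with the map and direct extra mapping. Under section 5, remapping is triggered when ablation falls on a predicted area, so someone in the room must know the predictions by then.
3. **Is the standard result fixed first?** The word traditional, applied to the map, and the remark about ablating an area the model also predicted both suggest that standard mapping comes first. No text shown requires it. Nothing withholds the predictions, locks a site list before the merge, or marks points taken because of the model. Section 7.3.3 keeps individual points, but the fields it gives as examples do not show why a point was taken.
4. **Could the enriched map differ from the standard one?** Section 2 hopes that studying predicted sites will show "which signals may indicate a critically important part of the VT circuit which traditional electroanatomical maps may miss". On the plan's own reasoning, the two maps need not be the same reference.

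**Sensitivity of the match rate (a unit conversion, not a bias estimate).** With 20 patients and s primary predicted sites each (s assumed), one relabelled site moves a pooled match rate by 100/(20 × s) percentage points:
- s = 1: 100/20 = 5.0
- s = 3: 100/60 = 1.7
- s = 5: 100/100 = 1.0

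How many labels would change is unknown.

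**Time.** Section 8 equates 10% with roughly 30 minutes, so the usual duration is about 30/0.10 = 300 minutes. If saving the map and list takes 5 to 10 minutes (assumed), that is 5/30 = 17% to 10/30 = 33% of the allowance, or 5/300 = 1.7% to 10/300 = 3.3% of the usual procedure.

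**Predicted sites the standard map did not sample.** Assume 60 sites (20 × 3), 30 of them matched, and 10% to 30% (6 to 18) unsampled. An unsampled site cannot be on the saved list.
- Counted as non-matches: 30/60 = 50.0%.
- Excluded: 30/54 = 55.6% with 6 unsampled; 30/42 = 71.4% with 18 unsampled.

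The choice of denominator can therefore matter, and excluding such sites raises the rate. It also costs precision. At a fixed 50% match and ignoring clustering within patients, the standard error √(0.25/n) is 6.5 points at n = 60, 6.8 at n = 54 and 7.7 at n = 42.

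**The case against.** The strongest reply has four parts.

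- **The flow chart in section 5 is not available and may set out the order.** This stands as a limit, so the point is confined to the text shown.
- **The extra mapping serves the second outcome, the electrical properties of predicted sites.** Section 5 says so, and nothing states that those points feed the reference for the first outcome. This also stands. A reader might infer that the final, enriched map is the planned reference. The documents leave that open, and equally do not rule it out.
- **Operator knowledge is inferred.** A reader might conclude that the operator will see the predictions before the first map. No text says so: section 6 returns the output for analysis, and section 7.3.1 concerns screening.
- **Safeguards exist.** High-density multipolar mapping is planned for everyone, which narrows any difference in sampling. Standard mapping guides the order of ablation, a point clarified after ethics review according to the amendment history. The model may not extend ablation, and section 8.1 says no important area is left untreated because the model missed it. These statements give real but partial protection to the ablation limit. They concern lesions and state an intended result, so they do not protect the judgement of which sites count as important.

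Re-reading the stored points later, by someone without the predictions, would help with labelling but would not undo uneven sampling.

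**Conclusion.** The concern holds in a limited form. The first outcome and the ablation limit depend on a standard-mapping result that the text shown does not require to be fixed before the predictions are revealed. A team could follow the text as written and still let prediction-directed sampling or unmasked judgement into the reference for the study's first aim.

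A reader might go further and infer that the match rate will be inflated, or that the ablation rule is defective or will be broken. The documents support neither. Bias arises only if the operator knows the predictions or the added points enter the reference, and its size and net direction cannot be estimated. The ablation rule itself is sound; what is missing is a record against which to check it. The sites per patient, minutes, unsampled share and match rate used above are all assumptions.

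The change should be made because it is cheap and uses steps already planned. Confidence is medium, chiefly because the flow chart could not be seen.

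**What to change.** 1. Complete the standard map without revealing the predictions to the operator. Save it with a time-stamped list of the sites judged important and the planned ablation targets.
2. Only then reveal the predictions, merge the model and do the extra mapping already planned, tagging each added point as model-prompted.
3. For primary predicted sites, use the saved list as the reference for the first outcome and show agreement with the final map beside it. The difference would measure the effect that cannot now be estimated. Report the match rate twice: with predicted sites unsampled by the standard map counted as non-matches, and with them excluded.
4. Report secondary sites separately. Section 1 describes them as sites "which can sustain VT in the post-ablation heart", so a map made before ablation is not their natural reference.
5. Log any lesion outside the saved list with its reason. Ablation decisions stay under the existing rule, with no new prohibition.

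**Cost.** The saving step takes a few minutes of an allowance that must also cover co-registration, extra mapping, remapping and any return to areas already visited. An existing team member other than the operator must hold the predictions until the list is saved. The reported match rate may move in either direction, and will be less precise where unsampled sites are excluded. No extra patients or visits are needed.

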6 STUDY SETTING

The study setting is a large tertiary centre hospital in London, St George's University Hospitals NHS Foundation Trust which serves a population of around 1.3 million. It also receives referrals from district general hospitals around it including in London, Surrey and Sussex. The patient population is diverse and referrals are made to a

specialist arrhythmia clinic from which suitable patients can be identified. The majority of recruited patients are expected to be outpatients who are symptomatic from VT despite optimal medical therapy. This will allow sufficient time to perform the cardiac MRI and to generate the computational model. In some scenarios, emergency admissions with symptomatic VT may be included if they are suitable for inpatient VT ablation and there is sufficient time for the MRI and computation analysis to take place prior to the VT ablation. All patient recruitment, consent, imaging and ablation will be performed at the single study centre.

The MRI images will be transferred to Johns Hopkins University in Baltimore, Maryland, USA for computational analysis and predictive modelling. This information will be securely transferred and on completion will be transferred back to the investigators for analysis.

7 SAMPLE AND RECRUITMENT

7.1.1 Inclusion criteria

- Adult inpatients admitted to St George's Hospital London with sustained ventricular tachycardia or outpatients identified from the arrhythmia clinic with significant monomorphic ventricular tachycardia noted on cardiac monitoring who:
 - Have sustained, monomorphic scar-dependent ventricular tachycardia
 - Are symptomatic
 - Failed, unable or unwilling to tolerate anti-arrhythmic medications
 - Able to have a cardiac MRI
 - Have a life expectancy > 1 year
 - At least 40 days following a myocardial infarction

7.1.2 Exclusion criteria

- Patients under the age of 18
- Patients who are unable to give informed consent
- Pregnant patients
- Unable to have cardiac MRI
- Prohibitive procedural risk
- Unable to tolerate the ablation procedure due to haemodynamic instability

7.2.1 Size of sample

We aim to recruit at least 20 consecutive patients. This is larger than any previous study in this area and will provide sufficient numbers to assess if the computational modelling is accurate in predicting sites of myocardium critical to sustaining ventricular tachycardia.

The current frequency of ventricular tachycardia ablation is roughly one patient every two to three weeks. Allowing for incomplete patient uptake to the study, this should permit the required number of patients to be recruited within 20 months. This allows sufficient time for data analysis and writing up of the results.

7.2.2 Sampling technique

Given the low volume of patients presenting with the appropriate ventricular arrhythmia, and the small sample size being targeted, the sampling technique will be of consecutive recruitment over a period estimated to be 20 months.

7.3.1 Recruitment

Potential patients will be identified from two sources: first, those presenting to the arrhythmia clinic at the primary centre with findings of sustained ventricular tachycardia who are symptomatic despite medical therapy. Clinicians at this arrhythmia clinic will be members of the study team. Suitable patients identified in this way would be referred for ventricular tachycardia ablation as standard of care. These patients will be highlighted to the site research team who are also part of patient clinical team who will then proceed to perform eligibility screening using the inclusion / exclusion criteria. The patients will have the study discussed with them and if consent is gained, they will be enrolled.

The second group of patients are those who present acutely to hospital (either directly to the primary study centre or referred from a different hospital for further management). The study investigators will be involved in the care of these patients as standard of clinical practice. However, if for any reason the study investigators are not involved in the care of the particular patient, the patient's clinical team can highlight and approach these potential participants before referring them directly to the study investigators. The same inclusion / exclusion criteria would apply and the investigators may explain the study to them, offer enrolment and gain consent for inclusion whilst inpatients.

The investigations and procedures, including the cardiac MRI and mapping and ablation of the tachycardia, are considered standard of care. Therefore no extra journeys, follow up appointments or costs will be incurred by the patients who choose to participate in the study.

